5.5.4.10 Time to Baseline TSC-associated Seizure Frequency

Blinded Phase only:

Time to baseline TSC-associated seizure frequency is defined as the number of reported days in IVRS, from Day 1, that it takes for the cumulative number of TSC-associated seizures experienced to be greater than or equal to the number of seizures (per 28 days) experienced during the baseline period and will be calculated as:

Date criterion was achieved – Date of Day 1 – Number of unreported days in IVRS between Day 1 and date criterion was achieved + 1

Patients who complete the trial without experiencing greater than or equal to the number of seizures (per 28 days) experienced during the baseline period, or who withdraw from the trial, will be censored at the earliest of:

- Day 99.
- The date of last dose as recorded on the ‘End of Treatment Study Outcome’ CRF page.

The exact day used for censoring will be the day obtained from above minus the number of unreported days in IVRS between Day 1 and the day obtained from above.

Time to baseline TSC-associated seizure frequency will be summarized on a continuous scale, by treatment arm, for patients in the ITT analysis set. The lower and upper quartiles will also be presented. The Kaplan-Meier estimates for the median time to baseline TSC-associated seizure frequency will be presented along with 95% CIs for the median and p-values from log-rank tests comparing each GWP42003-P arm with placebo. A Kaplan-Meier plot will also be produced.

The above will be repeated using Day 29 instead of Day 1 as the start day for counting the cumulative number of TSC-associated seizures.

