5.1.3.4 Treatment Period

The treatment period of the double-blind phase is defined as Day 1 to Day 113.

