2.3.3 Robustness to Withdrawn Patients

There were higher proportions of patients in each treatment arm that withdrew during the blinded phase treatment period when compared with placebo. In order to assess the robustness of the results, 2 analyses in the following sections are proposed.

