2.3.3.1 Time to 10th and 20th Seizure

Time from Day 1 to a patient experiencing their 10th and 20th or more seizure will be calculated as follows:

Date criterion was achieved – Date of Day 1 – Number of unreported days in IVRS between Day 1 and date criterion was achieved + 1

Patients who complete the blinded phase without experiencing greater than or equal to the corresponding number of seizures, or who withdraw from the blinded phase, will be censored at the earliest of:

- Day 113.
- The last recorded seizure day during the blinded phase treatment period.

The exact day used for censoring will be the day obtained from above minus the number of unreported days in IVRS between Day 1 and the day obtained from above.

The advantage of this proposed time to event analysis is that it is distinctly less sensitive to early withdrawals.

The time to corresponding event will be summarized on a continuous scale, by treatment arm. The lower and upper quartiles will also be presented along with the number of events and number of patients censored. In addition, the hazard ratio and 95% confidence interval, from a Cox proportional hazards model including treatment arm and stratified age group as covariates, will be presented along with a p-value from a log-rank test. A corresponding Kaplan-Meier plot will also be produced for both TSC-associated seizures and total seizures.

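### As worded, the time-to-event censoring rules in SAP 5.5.4.10 and addendum 2.3.3.1 censor every patient who withdraws, including those who had already reached the event

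*SAP*

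**What the plan says.** SAP 5.5.4.10 is an exploratory endpoint. "Time to baseline TSC-associated seizure frequency is defined as the number of reported days in IVRS, from Day 1, that it takes" to accumulate the patient's own baseline 28-day seizure number. The event time is computed from the date that number was met, less unreported days, and patients who later withdraw are not exempted. The censoring sentence then has two limbs. The first is "Patients who complete the trial without experiencing greater than or equal to the number of seizures (per 28 days) experienced during the baseline period". The second follows directly: "or who withdraw from the trial, will be censored at the earliest of" Day 99 and the date of last dose. The planned results are Kaplan–Meier medians and "p-values from log-rank tests comparing each GWP42003-P arm with placebo". No hazard ratio is planned in this section.

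Addendum 2.3.3.1, which is post hoc, uses the same construction for time to the 10th and 20th seizure. After the completers who stayed below the count, it continues "or who withdraw from the blinded phase, will be censored at the earliest of" Day 113 and a second item: "The last recorded seizure day during the blinded phase treatment period". This section does plan a hazard ratio, from a Cox model with age stratum as covariate, together with a log-rank p-value.

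Addendum 2.3.3 gives the reason for the analysis: "There were higher proportions of patients in each treatment arm that withdrew during the blinded phase treatment period when compared with placebo". Addendum 2.3.3.1 then recommends the time-to-event approach because early withdrawal should affect it much less.

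**The concern.** The condition of not having reached the event governs only the first limb of each sentence. A programmer who follows the text would censor every withdrawal, whatever happened beforehand. Nothing in either list of censoring days repairs this, because the date the criterion was met is in neither list. In the addendum the last recorded seizure day cannot come before the 10th seizure, so such a patient would be carried event-free past a 10th seizure that was recorded.

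Reaching the count is an unfavourable outcome. Discarding it helps whichever arm loses more such events, and the addendum says withdrawal was higher in both active arms. What is at stake is the log-rank tests and medians in 5.5.4.10, and the hazard ratio and log-rank test in addendum 2.3.3.1. The addendum analysis is offered as reassurance about unequal dropout, and under its own written rule it would be distorted by unequal dropout.

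**Working it through.** **Plan's own figures.** No event number, power or hazard ratio is stated for these analyses. The only design figure is 70 per arm for 90% power (SAP 3.2), used here only as the arm size. It reproduces: 2 × (1.960 + 1.282)² × 60² / 35² gives 62 per arm for a comparison of means. Dividing by the Wilcoxon relative efficiency gives 65 (3/π, normal data) to 72 (0.864, worst case).

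**One patient under the two readings (5.5.4.10).** Suppose every day is reported, the baseline count is reached on Day 20, and withdrawal and last dose fall on Day 60.
- Event first: (20 − 1) − 0 + 1 = 20, an event at 20 reported days.
- Literal: censored at the earlier of Day 99 and Day 60, which is Day 60. The event is lost and 40 event-free days are added.

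**Simulation.** The documents give 70 per arm and assumed reductions of 15% (placebo) and 50% (active). The rest is assumed:
- Withdrawal is 5% on placebo and 5–20% on active, independent of seizures, and falls on Days 1–28, 1–112 or 29–112.
- Baseline median is about 50 seizures per 28 days (log SD 1, rate floored at 8), with Poisson counts and patient-level variation.
- The Cox model is unadjusted for age. The literal reading censors at the withdrawal day.
- Bias uses 300,000 per arm; error rates use 4,000 trials of 70 per arm.

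**Events discarded** = 70 × withdrawal proportion × share of withdrawals that follow the event. At 15% active there are 70 × 0.15 = 10.5 withdrawals, and at 5% placebo 3.5. With withdrawals spread over Days 1–112 and no true effect, the discarded events are:
- baseline count: 6.6 active, 2.2 placebo (6.6 / 10.5 = 63% of active withdrawals);
- 10th seizure: 9.3 and 3.1 (89%);
- 20th seizure: 8.3 and 2.8 (79%).

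If withdrawals all fall in Days 1–28, only about 1 baseline-count event per 70 is lost at 15%.

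**Hazard ratio, literal reading, no true effect, placebo withdrawal 5%** (range over the three timings):

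| Active withdrawal | Baseline count* | 10th seizure | 20th seizure |
|---|---|---|---|
| 10% | 0.90–0.99 | 0.87–0.94 | 0.89–0.97 |
| 15% | 0.81–0.98 | 0.76–0.88 | 0.79–0.93 |
| 20% | 0.74–0.97 | 0.67–0.82 | 0.71–0.89 |

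*Illustrative only, since no hazard ratio is planned for this endpoint. For the baseline count the value nearest 1 is for withdrawal in Days 1–28.

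Counting events first gives 0.99–1.01 throughout. Equal 5% withdrawal gives 0.99–1.00 even under the literal reading.

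**Two-sided log-rank type I error, withdrawals spread over Days 1–112**, at 10, 15 and 20% active withdrawal: 7, 15 and 28% (baseline count) and 12, 30 and 55% (10th seizure), nearly all in favour of active. Counting events first gives 4.5–5.8%.

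**With the SAP's own 50% against 15% reductions**, the event-first hazard ratios are about 0.40 (baseline count), 0.65 (10th) and 0.64 (20th). The literal hazard ratio divided by the event-first one is:

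| Active withdrawal | Baseline count* | 10th seizure | 20th seizure |
|---|---|---|---|
| 5% (equal) | 1.00–1.07 | 1.02–1.09 | 1.01–1.05 |
| 10% | 1.00–1.02 | 0.97–0.98 | 0.96–0.98 |
| 15% | 0.96–1.00 | 0.88–0.93 | 0.88–0.96 |
| 20% | 0.90–1.00 | 0.79–0.88 | 0.81–0.93 |

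The direction can change because placebo patients then reach the event sooner, so a larger share of their withdrawals follow it. At equal 5% withdrawal, spread over Days 1–112, the baseline count loses 2.2 placebo events and 1.4 active ones.

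**The case against.** The strongest answer is that discarding events is one reading and probably not the intended one. Neither section says that an event already reached is set aside. Both define an event time for any patient who meets the criterion, and customary practice censors only those without one. The addendum's rationale also makes sense only if events before withdrawal count. This stands as evidence of intent. It does not cure the sentence, which censors withdrawals without condition. Nor is the literal reading far-fetched in this SAP: in 5.5.3.1.1, blinded-phase responder status is confined to patients who did not withdraw, so withdrawal overrides an observed outcome there.

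The second answer is that little depends on it. The endpoint in 5.5.4.10 is exploratory, the addendum is post hoc, and neither appears in the Table 3 hierarchy. Robustness of the primary result to withdrawal is examined separately, by the imputation and tipping-point analysis in 5.5.2.1.1 and by the worst-case analysis in addendum 2.3.3.2. This stands in full.

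A reader might go further and infer that the reported results are biased in favour of GWP42003-P. The documents do not support that. They do not show which reading was programmed, and they give neither the rates nor the timing of withdrawal. Under a real effect the bias can disappear or run against the drug.

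**Conclusion.** The wording is defective in both sections. Followed exactly, it discards observed events and defeats the stated purpose of addendum 2.3.3.1. More events are lost in the active arms if withdrawal is higher there and follows the event. The addendum establishes the first condition but not the second.

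The size is conditional on assumed withdrawal. At 15% active against 5% placebo with no true effect, the hazard ratio is about 0.76–0.88 for the 10th seizure and 0.79–0.93 for the 20th, where it should be 1. Log-rank error with withdrawals spread over Days 1–112 is about 15% for the baseline count and 30% for the 10th seizure. With the SAP's own reductions, the 10th-seizure hazard ratio is lowered by about 7–12% at 15% against 5%, while the baseline-count bias is small and can vanish or slightly reverse.

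Any statement about a hazard ratio concerns the addendum only; in 5.5.4.10 the log-rank tests and medians are affected. The primary and key secondary conclusions do not depend on this point.

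**What to change.** In both sections, replace the censoring sentence with: *A criterion reached on or before the censoring day is an event on the day it was reached, whether or not the patient later withdraws. Only patients who have not reached the criterion, whether they complete or withdraw, are censored at …*, followed by the list of days.

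The sponsor should also state which rule was programmed and, if it was the literal one, rerun the affected tables and plots. The cost is two sentences in each section and no new data. The downside is that the estimates may be less favourable to GWP42003-P if the literal rule was used.

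A separate matter to reconcile in the same edit: 5.5.4.10 stops at Day 99, while addendum 2.3.3.1 uses Day 113 and SAP 5.1.3.4 states "The treatment period of the double-blind phase is defined as Day 1 to Day 113".

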3. INVESTIGATIONAL PLAN

3.1 Trial Design

This multicenter trial consists of a randomized, placebo-controlled, double-blind phase followed by an open-label extension (OLE) phase.

Blinded Phase:

The blinded phase of the trial is a randomized, double-blind, parallel-group, 16-week comparison of two doses of GWP42003-P vs. placebo. Patients will complete a 1-week screening period and a 4-week baseline period before they are randomized to receive either 25 mg/kg/day GWP42003-P, 50 mg/kg/day GWP42003 P or placebo. Randomization will be stratified by age according to the following ranges: 1–6, 7–11, 12–17 years and 18–65 years. Patients will begin a 4-week dose escalation period, titrating up to their assigned dose, before continuing on a stable dose of blinded Investigational Medicinal Product (IMP) for 12 weeks.

Dose escalation for each patient is subject to the investigator's assessment of safety and tolerability. If a dose becomes poorly tolerated, the investigator may consider temporarily or permanently reducing the dose for the remainder of the trial.

Following completion of the blinded phase, patients will be invited to continue to receive GWP42003-P in an OLE.

Those patients opting not to enter the OLE will complete a 10-day taper period (down-titrating 10% per day for 10 days).

Open-label Extension Transition:

In order to maintain consistent exposure to IMP and maintain the integrity of the blind, patients will enter a 2-week blinded transition to the OLE. OLE IMP will be titrated up to 25 mg/kg/day whilst blinded IMP is simultaneously tapered down to zero. All patients will complete the transition and enter the OLE taking 25 mg/kg/day GWP42003-P:

- Patients from the placebo arm will titrate up to 25 mg/kg/day GWP42003-P.
- Patients from the 25 mg/kg/day GWP42003-P arm will continue to take 25 mg/kg/day GWP42003-P.
- Patients from the 50 mg/kg/day GWP42003-P arm will taper down (10% per day) to 25 mg/kg/day GWP42003-P.

Open-label Extension:

The OLE consists of a 3-week titration period followed by a maintenance period and a 10-day taper period. The initial OLE period will last for a maximum of 1 year.

Following titration according to the titration schedule, patients will continue with their optimal GWP42003-P dose. However, investigators may decrease the dose if a patient experiences intolerance, or increase the dose to a maximum of 50 mg/kg/day if required for better seizure control, until the optimal dose is found.

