5.1.3.6 Maintenance Period

The maintenance period of the double-blind phase is defined as Day 29 to Day 113.

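### Time to baseline seizure frequency: event-free patients are censored at Day 99 while events to Day 113 still count, which distorts the Kaplan-Meier tail and, in the Day 29 repeat, the median

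*SAP*

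**What the plan says.** Section 5.5.4.10 of the SAP defines the time as the "number of reported days in IVRS, from Day 1, that it takes for the cumulative number of TSC-associated seizures experienced" to equal or exceed the patient's baseline 28-day number. The event time comes from the date the criterion is met, less unreported diary days. No last day is set for events.

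Patients who complete without the event, or "who withdraw from the trial, will be censored at the earliest of" two dates: Day 99, and "The date of last dose as recorded on the" end-of-treatment form. Unreported days are subtracted here as well.

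The planned outputs are a continuous summary, log-rank p-values, a plot, and the median: "The Kaplan-Meier estimates for the median time to baseline TSC-associated seizure frequency will be presented along with 95% CIs for the median". A second version follows: "The above will be repeated using Day 29 instead of Day 1 as the start day".

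Elsewhere the follow-up is longer. Section 5.1.3.4: "The treatment period of the double-blind phase is defined as Day 1 to Day 113". Section 5.1.3.6: "The maintenance period of the double-blind phase is defined as Day 29 to Day 113". No text explains Day 99 or says that later events are ignored.

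**The concern.** Events and censoring are given different windows. Take two completers who are both event-free on Day 99. One reaches the baseline count on Day 105 and is kept at risk until then. The other never reaches it and is removed at Day 99, although observed to Day 113. The rule uses the outcome to decide who remains at risk, and Kaplan-Meier estimation does not allow that.

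The patients removed early are those with the largest sustained reductions. At stake are the right-hand end of the plot, where a reader looks for the proportion who never return to their baseline count, and the median with its confidence interval wherever more than half of an arm is event-free at Day 99. The text can also be programmed in two ways, with events after Day 99 kept or dropped, giving different curves from the same data.

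**Working it through.** **1. Day arithmetic.** Section 3.1 describes a 16-week blinded phase. 16 × 7 + 1 = Day 113, which reproduces the end of treatment in section 5.1.3.4. Day 99 = 14 × 7 + 1, two weeks earlier. For a completer the last dose falls at about Day 113, so Day 99 is the limit that applies.

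**2. Who has an event in the gap.** With a constant reduction *r*, the baseline 28-day count is reached after 28/(1 − *r*) days. Setting this equal to *d* days gives *r* = 1 − 28/*d*.

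| Start | To Day 99 | To Day 113 | Reductions whose event falls in the gap |
|---|---|---|---|
| Day 1 | *d* = 99, *r* = 71.7% | *d* = 113, *r* = 75.2% | 71.7% to 75.2% |
| Day 29 | *d* = 71, *r* = 60.6% | *d* = 85, *r* = 67.1% | 60.6% to 67.1% |

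**3. Effect on the curve.** The estimator is S(t) = ∏(1 − d/n). After Day 99 every patient left in the risk set will have an event, so at the last one d = n and S becomes 0. Worked examples with 70 patients, no withdrawals, no unreported days and no tied late events:

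- *From Day 1.* 31 are event-free at Day 99 (31/70 = 0.443) and 3 of them have a late event. As written: 0.443 → 0.295 → 0.148 → 0. With censoring at Day 113 the curve ends at 28/70 = 0.400.
- *From Day 29.* 41 are event-free at Day 99 (41/70 = 0.586) and 5 have a late event. As written, the first late event takes S to 0.586 × 4/5 = 0.469, so a median is reported just after the cap. With censoring at Day 113 the curve ends at 36/70 = 0.514 and the median is not reached.

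**4. Simulation (1,000 trials per setting, 70 per arm).** From SAP section 3.2: mean reductions of 15% (placebo) and 50% (active), SD 60%. Assumptions not in the SAP: lognormal rate ratios; baseline counts of at least 8 with mean about 57 per 28 days; withdrawal of 5% (placebo) and 12% (active); unreported days 0% or 3%; no events counted after withdrawal. Ranges are across the two unreported-day settings.

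| | From Day 1 | From Day 29 |
|---|---|---|
| Late events per arm, placebo / active | about 1.8 / 3.3 | about 4.5 / 4.6 |
| Event-free at Day 99, placebo / active | 0.08 / 0.44 | 0.19 / 0.58 |
| Curve ends at exactly 0, placebo / active | 80–85% / 94–96% | 98–99% / 98% |
| Mean final estimate as written, placebo / active | 0.01 / 0.02 | below 0.01 / 0.01 |
| Mean final estimate, Day 113, placebo / active | 0.06 / 0.39 | 0.13 / 0.50–0.51 |
| Active median changed | 10–16% of trials | 82–85% of trials |
| Active median not reached, Day 113 | 3–6% | 52–57% |
| Mean log-rank z, as written → Day 113 | −5.3 to −5.4 → −5.5 to −5.6 | −4.7 to −4.8 → −5.1 to −5.2 |

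In the Day 29 version the rule as written returned an active median beyond the 71-day cap in 71–89% of trials, typically 73–74 days.

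**5. Different assumptions.** With median rate ratios of 0.75 and 0.50, log-SD 0.8, a baseline median of 2 seizures per day and no withdrawals (400 trials), the final estimates (placebo / active) from Day 1 are 1% / 1% as written against 9% / 19%. From Day 29 they are 0% / 0% against 16% / 29%. The log-rank z moves by 0.2 to 0.3.

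**The case against.** The case for leaving this alone, or giving it little weight, has several parts.

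- *It is exploratory.* The analysis sits under section 5.5.4, is absent from the endpoint list in 3.3.3, and is outside the Table 3 hierarchy. No primary, key secondary or safety result depends on it. This stands and limits the weight of the point.
- *Not every curve falls to zero.* A reader might infer that all arms must. The documents do not support that: an arm with no event after Day 99 ends on a plateau. Under the assumptions of step 5, counting from Day 1, about 13% of placebo arms and 3% of each active arm have no late event, and all three curves reach zero in about 81% of trials. From Day 29 the figure is about 98%. Subtracting unreported days also moves some late events below 99, so the risk set there is essentially, not strictly, future events only.
- *The comparison is not invalidated.* A reader might infer that the log-rank result is unreliable or favours the drug. In these simulations the rule weakens the test slightly, and significance barely changes.
- *Day 99 is not wholly foreign to the SAP.* Section 5.5.2.1.1 cuts treatment into 14-day blocks with a final block of 15 days. 7 × 14 = 98, so that block is Days 99–113. This boundary serves imputation and gives no reason to censor there.
- *The addendum's Day 113 is weak support.* Its section 2.3.3.1 censors at Day 113 or the last recorded seizure day, but it is post hoc and concerns another endpoint. The point rests on sections 5.1.3.4 and 5.1.3.6 instead.

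Capping events at Day 99 as well would be coherent (mean z about −5.4 from Day 1 and −4.8 to −4.9 from Day 29), but section 5.5.4.10 does not say so.

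**Conclusion.** The censoring rule is wrong as written. It follows from the text and the product-limit formula, without any simulation, that an arm with an event beyond 99 on the analysis scale has an artificial drop, normally to zero. With 70 per arm such an event is likely, though not certain.

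The harm is specific. The tail of the plot is unreliable in both versions. The median and its interval are affected mainly in the Day 29 repeat, where a median that should often be not reached is usually reported as a value just after the cap. From Day 1 the active median changes in only 10–16% of simulated trials. The log-rank test loses about 0.2 (Day 1) to 0.4 (Day 29) in z.

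These sizes are illustrative. They depend on the assumed distribution of rate ratios, baseline counts and withdrawals: the correct active event-free proportion from Day 1 is 39% under one set of assumptions and 19% under the other. The direction is the same in both. The point is worth correcting but does not touch the trial's confirmatory conclusions.

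**What to change.** In section 5.5.4.10, for both the Day 1 and the Day 29 versions, replace Day 99 with Day 113 and add that one cut-off, the earlier of Day 113 and the date of last dose, applies to events as well as to censoring. Changing the number alone is not enough: events would still have no stated last day, and the last-dose limit would still cut off event-free patients but not events recorded afterwards.

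If Day 99 is really intended, state that patients whose event falls later are also censored at Day 99, and give the reason for setting aside the last two weeks.

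The cost is one or two sentences and a rerun of Tables 9.18.1 and 9.18.2 and Figures 9.16.1 and 9.16.2. No new data are needed.

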5.5 Efficacy Analysis

5.5.1 General Approach

Blinded Phase:

The primary analyses will use the ITT analysis set. Further analyses using the PP analysis set will also be performed for the primary endpoint and secondary endpoints where specified in the sections below.

The primary null hypothesis is:

- Following 16 weeks of treatment there is no difference in effect between the 25 mg/kg/day GWP42003-P treatment arm and the placebo treatment arm in terms of the change in number of TSC-associated seizures during the treatment period compared to baseline.

The null hypothesis will be rejected if there is statistical evidence of a difference between the treatment arms at the α -level of 0.05 for the primary endpoint.

Statistical hypothesis testing will be performed on the primary endpoint and other endpoints as appropriate. Each endpoint, including the primary will have 2 comparisons against placebo (25 mg/kg/day GWP42003-P vs. placebo and 50 mg/kg/day GWP42003-P vs. placebo). Also, 3 key secondary endpoints have been defined.

The primary and key secondary endpoints will be tested with their Type I error controlled by use of a hierarchical gate-keeping procedure, in the sequence given in Table 3. One must reject the null hypothesis of an endpoint at the level of 0.05 (2-sided) to test the hypothesis of the subsequent endpoint in the sequence at the level of 0.05 (2-sided). If a null hypothesis is not rejected then testing will stop and all subsequent analyses will be declared not statistically significant.

Table 3 Hierarchy for Analysis

Test	Endpoint	Treatment Comparison
1	Primary endpoint	25 mg/kg/day GWP42003-P vs. Placebo
2	1 st key secondary endpoint	25 mg/kg/day GWP42003-P vs. Placebo
3	Primary endpoint	50 mg/kg/day GWP42003-P vs. Placebo
4	1 st key secondary endpoint	50 mg/kg/day GWP42003-P vs. Placebo
5	2 nd key secondary endpoint	25 mg/kg/day GWP42003-P vs. Placebo

6	3 rd key secondary endpoint	25 mg/kg/day GWP42003-P vs. Placebo
7	2 nd key secondary endpoint	50 mg/kg/day GWP42003-P vs. Placebo
8	3 rd key secondary endpoint	50 mg/kg/day GWP42003-P vs. Placebo

All statistical tests will be 2-sided and use the 5% significance level.

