5.5.4 Exploratory Efficacy Endpoints

5.5.4.1 Composite Focal Seizure Score

Blinded Phase:

Composite focal seizure score will be calculated as the sum of:

- 1 × Number of focal motor seizures without impairment of consciousness or awareness.
- 2 × Number of focal seizures with impairment of consciousness or awareness.
- 3 × Number of focal seizures evolving to bilateral convulsive seizures.

Summaries and analyses of composite focal seizure score will be performed as per the primary endpoint (Section 5.5.2).

Sensitivity analyses will be performed on the ITT analysis set, repeating the above analysis, using data for only the maintenance period, titration period, and during each 4 weeks of the

maintenance period (Week 1 to 4, Week 5 to 8 and Week 9 to 12 of the 12 week maintenance period).

Analyses on the maintenance period, titration period and by each 4 weeks of the maintenance period will include only patients who have at least 7 days of seizure data within each period.

Open-label Extension:

Summaries will be performed for the OLE periods as described in the OLE portion of the primary endpoint section (Section 5.5.2).

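### The log-rank tests leave out the age strata used at randomization, and the addendum pairs an age-adjusted hazard ratio with an unadjusted p-value

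*SAP*

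**What the plan says.** SAP Section 3.1 states: "Randomization will be stratified by age according to the following ranges: 1–6, 7–11, 12–17 years and 18–65 years". The primary negative binomial model (Section 5.5.2), the responder CMH test (Section 5.5.3.1.1) and the ANCOVAs all use that age group.

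The time-to-event analyses handle it differently.

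- **SAP Section 5.5.4.10.** The event is a cumulative count "greater than or equal to the number of seizures (per 28 days) experienced during the baseline period". The plan gives Kaplan-Meier medians and "p-values from log-rank tests comparing each GWP42003-P arm with placebo", counted from Day 1 and again from Day 29. It mentions no strata.
- **SAP addendum Section 2.3.3.1.** The event is the 10th or the 20th seizure. The hazard ratio and 95% CI come from a Cox model with treatment arm and stratified age group, and the result "will be presented along with a p-value from a log-rank test". Again no strata are named.

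Section 5.5.4.10 falls under "5.5.4 Exploratory Efficacy Endpoints". Formal error control is confined to other endpoints: "The primary and key secondary endpoints will be tested with their Type I error controlled by use of a hierarchical gate-keeping procedure". The addendum describes its analyses as post hoc and makes no multiplicity adjustment (its Sections 1 and 2.3.1).

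**The concern.** There are two separate issues.

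**Coherence, in the addendum.** One result line would carry an interval that adjusts for age and a p-value that does not. The CI can exclude 1 while p exceeds 0.05, or the reverse. The plan gives no reason for having age in the estimate and not in the test.

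**Efficiency, in both places.** Stratified randomization balances the arms on age. If age also predicts the time to event, a test that ignores it overstates the variance of the treatment comparison. The type I error then falls below the nominal level ("All statistical tests will be 2-sided and use the 5% significance level") and power falls with it. How much depends on how strongly age predicts the particular endpoint.

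**Working it through.** **The plan's own figure.** The only power statement in the SAP (Section 3.2) is 90% with 70 per arm for a two-sided 5% Mann-Whitney-Wilcoxon test, with mean reductions of 15% and 50% and SD 60%. By Noether's formula, p = Φ(35 / (60√2)) = 0.660. The total is N = (1.960 + 1.282)² / (3 × 0.160²) ≈ 136.8, or 68.4 per arm, and power at 70 per arm is 90.6%. The figure reproduces. It says nothing about the log-rank tests, for which the SAP states no power.

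**General time-to-event check.**
- From the SAP: 70 vs 70, four age strata, two-sided 5%, follow-up to Day 113.
- Assumed: exponential times, placebo median 30 days, treatment hazard ratio 0.6, 10% dropout, evenly spaced age effects on the log-hazard.
- Each setting has 20,000 simulated trials, so the Monte Carlo error of a power near 75% is √(0.75 × 0.25 / 20,000) ≈ 0.3 points.

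| Hazard ratio, extreme age groups | Type I error, unstratified | Power, unstratified | Power, stratified | Change from not stratifying |
|---|---|---|---|---|
| 1.0 | 5.3% | 78.0% | 76.7% | +1.3 points |
| 1.7 | 4.9% | 76.8% | 77.0% | −0.2 |
| 2.2 | 4.3% | 73.9% | 76.4% | −2.5 |
| 3.8 | 3.2% | 66.0% | 75.2% | −9.2 |

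The stratified test's type I error stayed near 5% in these settings.

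**Section 5.5.4.10: target is the patient's own baseline count.** A seizure-count model was used with each patient's 28-day baseline count as target and censoring at Day 99. The treatment rate ratio of 0.7 is assumed. Each setting has 20,000 trials.

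| Assumed age effect | Type I error, unstratified vs stratified | Power, unstratified vs stratified |
|---|---|---|
| About sixfold on absolute seizure rate only | 5.4% vs 5.4% | 73.0% vs 72.5% |
| ±0.2 on log relative change (extreme groups differ by e^0.4 ≈ 1.5) | 4.7% vs 5.1% | 71.7% vs 72.8% |
| ±0.5 on log relative change (e^1.0 ≈ 2.7) | 3.0% vs 5.0% | 64.1% vs 72.6% |

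An age effect on absolute rate cancels, because target and accrual scale together. Only an age effect on relative change matters.

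**Addendum Section 2.3.3.1: fixed target of 10 or 20 seizures.** Here nothing cancels.
- Assumed: median baseline 55 seizures per 28 days, log-SD within age group 0.7 to 1.0, further between-patient log-SD 0.6 on treatment, placebo rate 0.85 of baseline, treatment rate ratio 0.55.
- Each setting has 3,000 trials. A rerun under the same assumptions agreed closely. Ranges cover both targets and both SDs.

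| Seizure-rate ratio, extreme age groups | Type I error, unstratified | Power lost by not stratifying |
|---|---|---|
| 1 | 4.6–5.6% | about none (within about 0.5 points) |
| 2 | 4.4–5.0% | about 1 point |
| 4 | 3.1–3.7% | about 5–6 points |
| 6 | 2.1–3.6% | about 9 points |

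At ratios of 4 to 6, the stratified and unstratified tests reached different verdicts in about 7–13% of trials. This indicates how often an age-adjusted interval and an unadjusted p-value might part company, though a Cox interval is not identical to a stratified log-rank test.

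**The case against.** The strongest case for leaving the plan alone has four parts.

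- **The harm is conditional.** A reader might infer that omitting the strata in itself makes these tests conservative and costs power for no benefit. The documents do not support that. The SAP gives no figure for how age relates to either endpoint, and with no age effect the unstratified test is valid and about 1 point more powerful. For Section 5.5.4.10 even a sixfold age difference in absolute rate costs nothing. This stands, and it limits the point.
- **Age is not adjusted for everywhere else.** The proportional odds models for the second key secondary endpoint (Section 5.5.3.1.2) and for the physician rating (Section 5.5.3.2.6), and the Wilcoxon sensitivity analysis (Section 5.5.2.1), also omit it. This stands. The log-rank tests are not a lone departure, so consistency alone is a weak argument.
- **Little rests on the result.** Section 5.5.4.10 is exploratory, the addendum is post hoc, both lie outside the hierarchy, and any error is toward conservatism. This stands and sets the priority.
- **The addendum already reports an age-adjusted hazard ratio and CI.** True, but this creates the mismatch: the p-value beside them comes from a different analysis.

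**Conclusion.** The point holds in a limited form. The log-rank tests do not use the randomization strata, and the addendum reports an age-adjusted interval with an unadjusted p-value. That mismatch follows from the text and needs no assumption about age.

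The loss of power does need one. It is most plausible in the addendum, because time to a fixed seizure count depends on absolute rate. Section 1.1 of the SAP makes a link with age believable, since it describes seizures becoming more frequent and severe through early childhood, but it does not quantify the link. In Section 5.5.4.10 the loss is probably small, because age would have to predict relative change from the patient's own baseline. A reader might take the 9-point loss as the expected cost there. It requires a nearly fourfold hazard ratio between extreme age groups on an outcome already scaled to the patient, and nothing in the SAP supports an effect of that size.

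All the power figures rest on the assumed distributions, treatment effects and age effects listed above. No confirmatory conclusion is affected.

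**What to change.** - **Addendum Section 2.3.3.1.** Stratify the log-rank test by randomized age group, or take the p-value from the same age-adjusted Cox model as the hazard ratio. The second option removes the mismatch completely. The first brings the test close to the Cox result.
- **Section 5.5.4.10.** Stratify the log-rank tests by randomized age group in both the Day 1 and the Day 29 versions.

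The change is a few words of text and one strata option in the program, with no new data. The statistical price is about 1 point of power if age turns out to be unrelated to the endpoint. The Kaplan-Meier curves can stay unstratified if a footnote says that the test is stratified.
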